	15.2.1 Paper CRFs	
	15.2.2 Electronic CRFs	3840
	15.3Data storage and access	
16	6 Protocol/GCP non-compliance	3840
17	7 End of Study definition	3841
18	3 Archiving	3941

19 Regulatory Considerations	
19.1 Ethical and governance approval	3941
19.2 Data Protection	3941
19.3 Indemnity	39
19.4Study sponsorship	4240
19.5 Funding	40
20 Study management	42
20.1 SMG (Study Management Group)	4143
21Quality Control and Assurance	441
21.1Monitoring	441
21.2Audits & inspections	441
22 Publication policy	441
23 Milestones	441
24 References	44

Glossary of abbreviations

CF	Consent Form		
CI	Chief Investigator		
CRF	Case Report Form		
CTM UHB	Cwm Taf Morgannwg University Health Board		
CTR	Centre for Trials Research		
CTU	Clinical Trials Unit		
CU	Cardiff University		
GCP	Good Clinical Practice		
НВ	Health Board		
HCRW	Health Care Research Wales		
HE	Health Economics		
HRA	Health Research Authority		
IC	Informed consent		
ICH	International Conference on Harmonization		
ICU	Intensive Care Unit		
ISF	Investigator Site File		
NHS	National Health Service		
PI	Principal Investigator		
PICS	Post Intensive Care Syndrome		
PIS	Participant Information Sheet		
QA	Quality Assurance		
QC	Quality control		
QL (QoL)	Quality of Life		
R&D	Research and Development		
REC	Research Ethics Committee		
RN	Research Nurse		
SMF	Study Master File		
SMG	Study Management Group		
SSC	Study Steering Committee		
SOP	Standard Operating Procedure		
VR	Virtual Reality		

1 Amendment History

The following amendments and/or administrative changes have been made to this protocol since the implementation of the first approved version.

Amendment No.	Protocol version no.	Date issued	Summary of changes made since previous version
NSA1	1.1	26.07.2023	The time restriction on two of the inclusion criteria for the Phase 1 focus groups have been relaxed from five years to ten years to maximise inclusivity of those who wish to share their experiences.
NSA2	1.2	28.08.2023	Addition of remote consent for ease for participants undertaking on-line focus groups for phase 1
SA1	2.0	12.01.2024	Addition of evaluation questionnaire at the end of Phase 1 focus groups
SA2	3.0	12.06.2024	Amendments for Phase 3 feasibility study based on outcomes of Phase 1 which include; - Inclusion/ exclusion criteria - Intervention content - Intervention delivery - Feasibility study design
NSA3	4.0	10.03.2025	Increase to phase 3 recruitment sample size

2 Synopsis

Short title	VR-READY			
Acronym	VR-READY			
Internal ref. no.	UID1363			
Funder and ref.	RfPPB-21-1870(P)			
Study design	Intervention Development and Feasibility			
Study participants	People who have been admitted to intensive care with critical illness and have/ have had ongoing recovery and rehabilitation needs and those healthcare professionals involved in the supporting that recovery and rehabilitation			
Planned sample size	Phase 1 – 8 ICU survivors/ family member, 8 HCPs Phase 3 – up to 25 participants (plus all willing research delivery staff)			
Planned number of sites	1			
Inclusion criteria	 The inclusion criteria for Phase 1 focus groups are: people with a previous admission to critical care within the last ten years family members/ carers of a patient with a previous admission to critical care in the last ten years. NHS employees involved in the care of critical care patients in ICU NHS employees involved in the care and recovery of patients discharged from critical care (e.g. physiotherapists, psychologists, occupational therapists etc.) The inclusion criteria for the Phase 3 feasibility study are; Current hospital admission involving a stay in critical care, requiring organ support for more than 48 hours OR the / relative/loved one of someone admitted to critical care and is participating in the Phase 3 study FOR ICU PATIENTS ONLY: If normal vocalization is not possible (due to tracheostomy) then the participant must have an established method of communication with bedside nurse/ ward staff 			
Exclusion criteria	The exclusion criteria for the Phase 1 focus groups are; - Any person unable to provide informed consent - Any person unable to communicate in English The exclusion for the Phase 3 feasibility study are; - FOR PATIENTS ONLY: Any person experiencing delirium as assessed daily using CAM-ICU - A history of severe motion sickness - A history of photosensitive epilepsy - Any physical or anatomical contraindications to using VR headsets (e.g. severe visual or hearing impairment, major skull or facial surgery) [This does not include those that may require assistance to place the headset due to muscle weakness from ongoing admission.] - Any person unable to communicate in English			
Follow-up duration	Phase 1 – 6 months Phase 3 - up to 12 weeks			
Planned study period	24 months			
Primary objective	Phase 1;			

Phase 3; - Determine the feasibility and acceptability of selected outcome measures for use in future efficacy and cost-effectiveness studies for ICU recovery -Generate a framework for DR.VR adaptation that can be applied to other healthcare settings Primary outcomes Phase 3 Study: Feasibility Secondary outcomes To be determined by the Phase 1 activities	Secondary objectives	 Determine the recovery pathway of ICU survivors; including identification of critical components underpinning effective recovery and facilitators and barriers affecting these. Phase 2; Co-produce a VR mediated home based intervention to aid recovery in ICU survivors Phase 3; Determine feasibility and acceptability of the developed intervention in a home-based setting Phase 1; Determine applicable outcome measures of relevance to all stakeholders
Primary outcomes Phase 3 Study: Feasibility		- Determine the feasibility and acceptability of selected outcome measures for use in
Secondary outcomes To be determined by the Phase 1 activities	Primary outcomes	Phase 3 Study: Feasibility
	Secondary outcomes	To be determined by the Phase 1 activities

[figure not shown]

3 Study summary & schema

3.1 Study schema

3.2 Participant flow diagram

[figure not shown]
Participant flow for the Phase 3 feasibility study

3.3 Study lay summary

People admitted to intensive care (ICU) often experience ongoing health problems once they leave and have returned home. This is described as Post Intensive Care Syndrome (PICS) and can include problems with memory and thinking, physical impairments and reduced psychological wellbeing. This can result in a reduced quality of life, which also affects family members and friends. Although improvements have been made in caring for people within ICU, there is no standard approach to care after leaving ICU to support patients' recovery. A lack of staff and resources have also been a barrier to standard post -ICU care. With the recent increase in admissions to ICU, there is an urgent need to find ways of supporting the recovery of people with PICS that is readily available to patients. A recent review of how to combat PICS suggested that home-based and virtual care plans would be one way of making sure that as many people as possible could take advantage of rehabilitation support.

Immersive virtual reality (VR) can be accessed simply with an easy -to-use headset. VR has already been shown to be useful in helping relaxation and in combatting pain and anxiety. We think that VR might help support people recovering from critical illness and this study is aimed at developing a VR program (intervention) that can address the current inadequacies in post-critical care support.

In order to do this, we are proposing a three stage program of research. First, we need to understand what the recovery journey looks like. We will conduct a series of focus groups with ICU survivors, their family members and healthcare professionals involved in the care and rehabilitation of ICU patients. In these sessions, we will explore what the patient recovery journey looks like and what the critical parts of recovery are. We will also work with these groups to determine, in terms of recovery, what is important to measure (known as outcomes) to find out whether or not a virtual reality-based intervention works.

The second stage will use data from the focus groups which will then be used to alter an existing VR set-up (DR.VR) to specifically support the recovery of ICU patients, working with previous ICU patients and their family members to inform the design. We will also ask this group what features need to be included when testing the intervention and use this input to design the next stage of the project.

In the third part of the study, we will test the adapted VR intervention in a small group of patients who have previously been admitted to ICU. The aim of this study will be to see if using a VR intervention is possible and if people are happy and willing to use it. We will also explore how acceptable participants find the outcomes selected from the earlier focus groups. We will do this by interviewing participants about their experience. We will also interview the healthcare professionals involved in the care and rehabilitation of these participants to gather their views on the VR intervention. The interview data will be analysed qualitatively to provide an in-depth understanding of the intervention and outcomes. This data can then be used to inform the design of larger studies in the future to test how effective the VR intervention is at supporting the recovery of ICU patients.

At the end of the study, we will share the results with all of the study participants and more widely through appropriate web pages, social media and organisations concerned with the care of ICU patients.

4 Background

Improvements in knowledge and new therapeutic interventions have brought about increased survival rates from critical illness. However, despite prominence as an outcome measure in critical illness research, survival is not the sole outcome of importance to patients, with quality of life following critical illness increasingly recognised as a cornerstone of the recovery journey. It is therefore essential that critical illness research also focuses on survivors' quality of life.

Post intensive care syndrome (PICS) is common following an ICU stay and can be significantly debilitating. Characterized by cognitive, psychological and physical impairments, PICS profoundly impacts the lives of patients and their families: a third of patients do not return to work, another third are unable to do the same work. A quarter of patients still require assistance in activities of daily living a year after ICU admission often affecting the working lives of family members¹. It has been suggested that "critical illness associated with ICU admission should be treated as a lifetime diagnosis with associated excess mortality, morbidity and the requirement for ongoing health support"². In terms of prudent healthcare, large investments made during intensive care are only sustained when continued support is in place following discharge³.

There are several well described interventions currently used as the gold standard in PICS prevention during an ICU stay (choice of sedation drugs, sedation breaks, spontaneous breathing trials and early mobilisation) but there is no standardised approach to post -ICU care. Despite published NICE guidance on rehabilitation after critical care in 2009, with quality standards in 2017^{4,5} currently less than a third of ICU patients in the UK receive dedicated outpatient follow-up 2-3 months after ICU discharge⁶⁻⁸. A recent editorial in the British Medical Journal highlighted the lack of adequate post-ICU rehabilitation, emphasising the serious consequences for individuals and association of increasing costs to the NHS, particularly from unplanned readmissions. It stated that research to determine the most clinically and cost -effective rehabilitation strategies should be a priority, with collaboration between patients, funders and researchers to identify and address evidence gaps⁸.

UK Guideline for the Provision of Intensive Care Services (GPICS2)³ explains that leaving ICU is only the start of a long recovery process which may take months to years, and that there may be considerable residual impact on patient's morbidity and longevity. It also emphasizes the need for further research in this area. Recommendations include the monitoring of outcomes and recovery progression using measures appropriate for the stage of recovery, individual therapy and dependent on local resources including personnel, equipment and finance and additionally a specialist rehabilitation coordinator to facilitate oversight of the rehabilitation pathway. Delivery of services to these standards, especially after leaving hospital, is rare. A recent survey found that delivery to these standards occurred in only 18% of sites⁹ mainly due to a lack of funding and staff. The need to think of alternative strategies to deliver therapeutic interventions such as home-based services and virtual platforms to "ensure maximum inclusivity for patients into rehabilitation programs" has been

considered against the limited availability of resources¹⁰. However, the need for careful management to prevent issues such as digital poverty and literacy from limiting access was also mentioned. GPICS2 further recommends a rehabilitation plan addressing all relevant domains for patients including physical, functional, communication, social, spiritual, nutritional and psychological elements³ whilst simultaneously acknowledging that "the service-user voice is often missing in shaping research" in this area³. The current literature highlights that research into improving post-ICU recovery is essential and is strongly suggestive that the development of accessible, inclusive interventions to aid recovery should be of central prominence.

One potential method of doing this is using immersive virtual reality (VR). VR has been utilised in a variety of healthcare settings and has demonstrated promise in a range of clinical areas¹¹⁻¹⁴. Immersive VR been shown to be beneficial in reducing pain and anxiety, to help with relaxation, and been found to be safe and acceptable to intensive care patients¹⁵. Additionally, VR has shown equal effectiveness to conventional therapies in rehabilitation after stroke, with the added benefits of independent use, more accurate feedback and the ability to stimulate users more than traditional methods⁹.

4.1 Rationale for current study

Building on our previous work employing immersive VR in an ICU setting^{15,16} we believe that VR provides a unique opportunity to develop an effective, safe and acceptable intervention to aid recovery in PICS affected patients. However, there remain a number of unknowns as to how this might be realistically achieved in a real-world setting. Therefore, we are proposing a program of work which centres service users in understanding what elements would be required to aid recovery and how we may best measure the effectiveness of any such intervention in future studies. We will research the patient experience of recovery from critical illness to identify intervention priorities and outcome measures considered important and acceptable to ICU survivors, their loved ones and relevant ICU and rehabilitation staff. Working with a local Welsh business (Rescape), we will adapt an existing, CE marked VR kit (DR.VR) already in use within the NHS to co-produce a VR-mediated intervention to aid recovery and rehabilitation following an ICU stay. The resulting intervention will then be tested in a group of patients admitted to ICU to examine the feasibility and acceptability of the intervention and its delivery..

This proposal will contribute to understanding of advancing health technologies and their translation and implementation for patient benefit across the NHS. We are focusing here on recovery from PICS, but we will also identify the critical aspects of DR.VR adaptation and intervention development for application to other healthcare priorities and settings. This framework can then be used in the development of interventions aimed at promoting physical and psychological well-being for a variety of patients, which will have wide-reaching benefits across the NHS.

5 Study objectives/endpoints and outcome measures

The overall aim of this study is to co-design an accessible VR mediated intervention to improve inpatient experiences as an aid to recovery in people admitted to critical care. This will occur in 3 phases and the study objectives are defined accordingly.

5.1 Primary objectives

Phase 1;

- Determine the recovery pathway of ICU survivors; including identification of critical components underpinning effective recovery and facilitators and barriers affecting these.

Phase 2;

- Co-produce a VR mediated intervention to improve in-patient experiences as an aid to recovery in ICU survivors

Phase 3;

- Determine feasibility and acceptability of the developed intervention within a hospital setting

5.2 Secondary objectives

Phase 1;

- Determine applicable outcome measures of relevance to all stakeholders

Phase 3;

- Determine the feasibility and acceptability of selected outcome measures for use in future efficacy and cost-effectiveness studies for ICU recovery
- -Generate a framework for DR.VR adaptation that can be applied to other healthcare and at-home settings

5.3 Primary outcomes measure(s)

For the phase 3 study, the primary outcome measure will be feasibility as determined by: recruitment, retention, data completeness and intervention adherence. Each measure of feasibility will be assessed according to the pre-defined criteria outlined below.

Variable		Progression Criteria		
		Red	Amber	Green
	No approached willing to participate	<5%	5-19%	20%

Recruitment	No screened actually recruited	<50%*	50-74%	75-100%
	No. recruited	< 6 in total	6-12	12-25
Retention	No of partially active trial participants at			
	primary end point	<50%	50-79%	80%
Adherence	Completion of intervention sessions*	<50%	50-79%	80%
Data	Completion of baseline measures	<50%	50-79%	80%
Completeness	Completion of follow up measures	<50%	50-69%	70%

^{*}to be refined following intervention development in Phase 1 and Phase 2.

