9.1 Participant identification

Phase 1

Participants for the focus groups (ICU survivors and/ or their relatives and care partners) will be identified through the local ICU survivors support group, of which our PPI co-applicant is a member. Other participants will be identified and invited by the local research team within the health board. Additionally, ICU survivors may be identified and invited through the UK wide support network, ICU Steps through their mail out or other electronic communications such as twitter.

Health care professionals will be identified locally by the research team and study collaborators. Additional participants may be sought through advertising through professional networks.

Participants interested in taking part in the focus groups will be asked to register their interest by emailing the study team. They will be then sent a participant information sheet with details of the focus groups to be held.

Phase 3

Phase 3 participants will be identified by the local PI and research team in the critical care wards including ICU and High dependency unit (HDU). This is an active research centre where daily participant screening for inclusion in research is routine practice. Potential participants will be provided with a study information sheet, which has been co-produced by ICU survivors following discussion with their consulting clinician or member of the research team. Those interested in taking part can confirm their interest with the research team.

The data collected in Phase 1 indicated that ICU patient family members and support partners may also experience significant anxiety and issues with well-being as a result of their loved one's admission to ICU. At the suggestion and input from those with lived experience, the intervention will also be offered to those family members and support partners. Inclusion of this group will be in two ways- as users of the VR intervention and/or as providers of information relating to intervention delivery and usage in their family member/ loved one.

This group will be identified as those visiting patients within the ICU or HDU who have already provided consent to be part of phase 3. Potential participants will be approached as above if their family member/ loved one has agreed to take part in the study.

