9.2 Screening logs

A screening log of all ineligible and eligible but not consented/not approached will be kept at the site to provide information on the feasibility of recruitment. For those approached to participate in the

phase 3 feasibility study will be asked to provide a reason for non-participation, but if the person does not want to provide a reason, this will not be mandated and will be marked as 'no reason given'. Free text answers will be stored in the screening log for subsequent analysis. When at site, logs may contain identifiable information but this **must** be redacted prior to being sent to the CTR. The screening log should be sent to the CTR study personnel every 2 months (see section 19 for further detail on data monitoring/quality assurance).

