9.3 Recruitment rates

We will aim to recruit up to 25 participants from ICU at an expected rate of 3.5-4 per month. Family member/ loved ones will be additional to that target sample and we do not expect to include more than 15 family members/ loved ones.

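### Two recruitment rows of the Section 5.3 progression table cannot be scored unambiguously: 12 recruits is both amber and green, and the denominator of the recruited-among-screened row is undefined

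*Protocol*

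**What the plan says.** Protocol Section 5.3 makes feasibility the primary outcome of Phase 3, with recruitment as its first component, and announces that "Each measure of feasibility will be assessed according to the pre-defined criteria outlined below". The recruitment part of the table has three rows:

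- Row 1, "No approached willing to participate": red below 5%, amber 5-19%, green at 20% (read here as 20% or more).
- Row 2, "No screened actually recruited": red below 50%, amber 50-74%, green 75-100%. The red limit carries an asterisk, explained under the table as "to be refined following intervention development in Phase 1 and Phase 2".
- Row 3, the number recruited: red below 6, amber 6-12, green 12-25.

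The table does not define *screened*. Three other places bear on it. Section 9.1 describes a centre where "daily participant screening for inclusion in research is routine practice", with the information sheet given to potential participants identified there. Section 9.2 adds, as a source on how feasible recruitment is: "A screening log of all ineligible and eligible but not consented/not approached will be kept at the site". Table 2 in Section 11.3.1 lists informed consent and eligibility assessment together in the Screening column. On numbers, Section 9.3 says: "We will aim to recruit up to 25 participants from ICU at an expected rate of 3.5-4 per month".

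**The concern.** The three rows are meant to turn recruitment into a colour fixed in advance. Row 3 gives two colours to one possible result. Row 2 can give opposite colours to the same recruitment, depending on which group is taken as its denominator, and under one of the two available readings it works against row 1: a level of willingness that row 1 calls green produces red on row 2 by arithmetic alone.

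What is at stake is whether the primary outcome is really pre-specified. If the denominator is settled only once the counts are known, the colour of row 2 is chosen with the result in view. Section 13.1 plans no quantitative analysis of the feasibility study, so these bands are the main numerical decision rule the protocol has.

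**Working it through.** The protocol derives no figure here, so there is nothing to reproduce. The check is whether the bands are disjoint and whether rows 1 and 2 can agree.

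**Row 3.** Taking every whole number from 0 to 25: 0-5 is red, 6-11 amber only, 12 both amber and green, 13-25 green only. The single overlap is at 12, and there are no gaps.

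**Row 2, reading A: screened means everyone screened (Sections 9.1 and 9.2).** Let S be the number screened, A approached, W willing and R recruited, all counted in the same group of patients.

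- Screening precedes the approach, and the log includes ineligible and non-approached people, so A ≤ S.
- Section 9.4 treats only consented and enrolled people as participants, so R ≤ W.
- Hence R/S ≤ W/A: row 2 can never exceed row 1.

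| Willing among approached | Row 1 | Best possible on row 2 |
|---|---|---|
| 5-19% | amber | red |
| 20% to just under 50% | green | red |
| 50% to just under 75% | green | amber |
| 75% or more | green | green |

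The last line needs nearly everyone screened to be eligible and approached. At exactly 75% it needs A = S and R = W.

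With 25 recruits:

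- At 20% willingness, the number approached is at least 25/0.20 = 125, so row 2 is at most 25/125 = 20%, which is red.
- Green on row 2 allows at most 25/0.75 = 33.3, that is 33, screened.
- Avoiding red on row 2 allows at most 25/0.50 = 50 screened.

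With 12 recruits at 20% willingness, 12/0.20 = 60 are approached, against limits of 12/0.75 = 16 screened for green and 12/0.50 = 24 for non-red.

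A count of all whole-number combinations with up to 150 screened and exactly 20% willing gave 2205 cases. Row 2 was red in every one.

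**Row 2, reading B: screened means willing people taken on to eligibility assessment (compatible with Table 2).** The denominator is now W or a part of it, and the bound above no longer applies. The same recruitment scored both ways, each at 20% willingness:

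| Approached | Willing | Recruited | Row 2, reading B | Row 2, reading A (at most) |
|---|---|---|---|---|
| 125 | 25 | 25 | 25/25 = 100%, green | 25/125 = 20%, red |
| 160 | 32 | 25 | 25/32 = 78%, green | 25/160 = 16%, red |
| 100 | 20 | 15 | 15/20 = 75%, green | 15/100 = 15%, red |

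Row 1 is green throughout. Only the meaning of *screened* moves row 2 from red to green.

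**The case against.** The best defence is that rows 1 and 2 do not conflict at all. They can be read as a funnel: approached, willing, assessed for eligibility, recruited. Table 2 supports this by placing consent and eligibility assessment together under Screening, and a green band of 75-100% is far more natural on that reading. Section 9.2 describes the log without saying that it supplies row 2's denominator. This stands, and it means that a flat contradiction between the rows cannot be asserted. It does not rescue the table, because the funnel reading is not written there, and it sits poorly with screening that precedes the approach and with a log kept to inform the feasibility of recruitment.

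A second defence is the asterisk, which marks the row 2 red limit as provisional. That does not help either. The same section calls the criteria pre-defined, the Amendment History records that the Phase 3 design was already amended on Phase 1 outcomes, and refining a cut-off would not define a denominator. The asterisk does not touch row 3.

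A third is that the overlap at 12 matters only if exactly 12 are recruited. That is true, and it limits the weight of the point, but nothing else in the protocol resolves it.

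A reader might go further and infer that the study cannot reach any coherent decision on recruitment. The protocol does not support that: each measure is assessed against its own criteria, no single red is said to stop progression, and rows of different colours can be reported side by side.

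**Conclusion.** Two defects stand. The overlap at 12 is certain from the printed bands. The undefined denominator of row 2 is also certain. Its consequence is conditional: on the all-screened reading, willingness of 20-49% is green on row 1 and must be red on row 2, and 50-74% is amber at best; on the willing-and-assessed reading, the rows agree. The forced red rests on that first reading and on both rows counting the same people. It does not extend to every green result on row 1.

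Three further criticisms might be drawn from the same rows, and the documents do not carry them:

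- Green starting at 12 of 25 (48%) is not an error. The sample is stated as up to 25, a pragmatic ceiling, and accepting 12 is a design choice.
- The absence of a recruitment window cannot be asserted. Section 13.1 refers to a given timeframe, and the milestones figure is not visible in the text reviewed.
- Daily screening activity says nothing about how many new patients are screened. No admission or screening volume is given, so the limits of 33 and 50 screened cannot be called implausible on that ground.

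This should be fixed. It affects the scoring of part of the primary outcome, not the design or conduct of the study.

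**What to change.** Amend the Section 5.3 table before Phase 3 data are reviewed:

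1. **Row 3:** make the bands disjoint. Amber 6-11 with green 12-25, or amber 6-12 with green 13-25, both remove the overlap and leave no gap. The choice belongs to the study team.
2. **Row 2:** state the denominator as people who said they were willing and were then assessed for eligibility, and keep the 50% and 75% cut-offs. People found ineligible at that step should stay in the denominator. Restricting it to those both eligible and willing would put the rate near 100% by construction, since Section 9.5 takes consent straight to registration. If all screened patients are meant instead, reset row 2's cut-offs so that they are consistent with row 1.
3. **Asterisk on row 2:** finalise the limit or remove the mark.
4. **Reporting:** give the counts screened, approached, willing and recruited as a descriptive funnel, without bands.

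The cost is a few words in one table. The Section 9.2 log already covers people who were ineligible, not approached or not consented. The team should check that it also identifies those who were willing and then assessed, and add that field if it does not.

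### The amber and green bands for number recruited overlap, so a final count of exactly 12 is graded both colours on a primary-outcome criterion

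*Protocol*

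**What the plan says.** Protocol section 5.3 names feasibility as the Phase 3 primary outcome. It is judged on recruitment, retention, data completeness and adherence, each against a pre-defined progression table.

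- **Number recruited:** "No. recruited < 6 in total 6-12 12-25", in the order red, amber, green.
- **Retention:** "primary end point <50% 50-79% 80" percent.
- **Baseline completeness:** "Completion of baseline measures <50% 50-79% 80" percent.
- **Follow-up completeness:** "Completion of follow up measures <50% 50-69% 70" percent.

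A footnote says that asterisked entries will be refined after Phases 1 and 2. The asterisk stands on the red cell of the screened-to-recruited row and on the adherence row. It does not stand on number recruited, retention or either completeness row.

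Section 9.3 sets the target at up to 25 ICU participants, at 3.5 to 4 a month, with relatives on top of that target. Section 13.3 says that no SAP will be written. The protocol contains no rule for ties or for rounding.

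**The concern.** A traffic-light table works as a pre-defined criterion only if each possible result has exactly one colour. In the count row, amber and green share the endpoint 12, so that result has two. Someone would then have to choose the colour after seeing the total, which is the discretion that setting criteria in advance is meant to remove.

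The percentage rows raise a related, weaker question. The red/amber edge is written as a continuous cut (below 50%, then from 50%). The amber/green edge is written in whole percents (79 then 80, or 69 then 70). With small denominators a result can lie between the two numbers, and its colour then depends on a rounding convention that is not stated.

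Where the cuts should lie is not in question here, only how they are written.

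**Working it through.** There is no sample-size or power figure to reproduce, because section 13.1 calls the target of up to 25 pragmatic. The check is whether each result falls in exactly one band.

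**1. Number recruited** (bands from section 5.3; whole counts 0 to 25)

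- Red, below 6: 0 to 5, which is 6 values.
- Amber, 6 to 12: 7 values.
- Green, 12 to 25: 14 values.
- Sum: 6 + 7 + 14 = 27 assignments for 26 possible counts.

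No count is left out, so one is counted twice. It is 12, which meets both 6 ≤ k ≤ 12 and 12 ≤ k ≤ 25.

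Twelve is an ordinary value for this study. At the rate in section 9.3 it is reached after 12/4 = 3.0 to 12/3.5 = 3.4 months. As a final total it is 12/25 = 48% of the maximum, so it would arise if recruitment ran at about half of plan.

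**2. Retention and data completeness** (assumption: the denominators are ICU participants, n ≤ 25)

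A result x/n lies between amber and green when a < 100x/n < a + 1, where a is the last amber percent. All x/n with n ≤ 25 were enumerated with exact fractions.

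| Row | a | Results between bands | Unrounded | Whole percent | Colour if rounded |
|---|---|---|---|---|---|
| Retention; baseline completeness | 79 | 19/24 | 79.17% | 79% | amber |
| Follow-up completeness | 69 | 9/13 | 69.23% | 69% | amber |
| Follow-up completeness | 69 | 16/23 | 69.57% | 70% | green |

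For n = 24, for example, x must lie strictly between 0.79 × 24 = 18.96 and 0.80 × 24 = 19.20, which only 19 does. For n = 23 in the follow-up row the limits are 0.69 × 23 = 15.87 and 0.70 × 23 = 16.10, which only 16 meets.

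Rounding closes all three gaps. For 19/24 and 9/13 it gives the colour that an unrounded cut at 80% or 70% would give. For 16/23 it does not: the rounded value is green, while 69.57% is below 70%.

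**3. After the change**

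With 6-11 / 12-25, or with 6-12 / 13-25, the sum in step 1 is 26 and every count has one colour. With amber from 50% to below 80% and green from 80% (70% for follow-up), 19/24, 9/13 and 16/23 are all amber.

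**The case against.** The best defence concerns the percentage rows. Bands written 50-79 then 80 are commonly meant as whole percentages, and read that way every result has one colour. A rounding convention is also a detail that often sits in an analysis plan. This largely stands. It would be too strong to say flatly that some results fall in no band: that is true only of unrounded values, and what is missing is a stated convention. The defence is limited by section 13.3, which says that no SAP will follow, and by 16/23, where the convention changes the colour.

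A reader might also infer more than the table supports:

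- **Adherence.** The row counts sessions ("Completion of intervention sessions* <50% 50-79% 80" percent), not participants, and is marked for refinement. The participant fractions above do not carry over to it.
- **Denominators up to 40.** Adding the 15 relatives would give more in-between fractions. But section 9.3 calls relatives additional to the target sample, and section 5.3 does not say that they enter these denominators.
- **Green meaning exactly 80% or 70%.** A sign may have been lost when the table was read from PDF. Nothing here depends on it, since the interval between 79 and 80 remains when green is read as 80% or more.

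Finally, the protocol attaches no stated action to a colour and describes its analysis as qualitative, so the practical consequence is modest. That bears on how much the point matters. None of these arguments touches the overlap at 12: it concerns whole counts, both ranges are printed intact, and the row carries no refinement mark.

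**Conclusion.** The number-recruited row is wrong as written. One attainable total out of 26, namely 12, is graded both amber and green on a primary-outcome criterion, and nothing in the protocol resolves it. This rests on no assumption beyond the printed bands.

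The rounding point is secondary. It assumes participant denominators of at most 25, which section 5.3 does not state for the completeness rows. On that assumption it concerns one fraction (19/24) for retention and for baseline completeness, and two (9/13 and 16/23) for follow-up completeness. Only 16/23 gets a different colour from whole-percent rounding than from the unrounded cut.

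The point is minor in scale. It does not show that the thresholds are badly placed or that the feasibility assessment as a whole is unsound.

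**What to change.** Edit the table in section 5.3:

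- **Number recruited:** make the bands non-overlapping, as 6-11 amber and 12-25 green, or 6-12 amber and 13-25 green. Which colour 12 takes is the study team's choice; it should be made before the final count is known.
- **Retention and baseline completeness:** red below 50%, amber from 50% to below 80%, green 80% or more.
- **Follow-up completeness:** red below 50%, amber from 50% to below 70%, green 70% or more.
- **Rounding:** add a line saying that percentages are graded unrounded. A stated whole-percent rule would also give each result one colour, but would make 16/23 green.

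The cost is the table edit only. Sample size, data collection and the position of the percentage cuts are unchanged.
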